We will examine the impact of repeated episodes of hypoglycemia on brain glycogen content and turnover in healthy controls. As in Aim 1a, subjects will be studied both after preconditioning with euglycemia and after preconditioning with recurrent hypoglycemia to induce HAAF, done in random order separated by a minimum of 6 weeks (Fig. 6). Female controls will have their two studies two months apart in order to control for phase of menstrual cycle.

The hypoglycemia preconditioning and euglycemia preconditioning protocols will be identical to those described in Aim 1a, with the first MRS session to measure ^{13}C -glycogen level in the afternoon on Day 2 (Fig. 6). At minute +30 following the end of the last hypoglycemic or euglycemic clamp, a bolus injection of 20 g of $[1-^{13}\text{C}]$ glucose (prepared as 20% weight/volume D-glucose in water with 50% isotopic enrichment) will be administered to subjects regardless of their preconditioning protocol. Twenty minutes later a continuous infusion of 2 mg/kg/min of $[1-^{13}\text{C}]$ glucose (prepared as 20% weight/volume D-glucose in water with 25% isotopic enrichment) will be started and then adjusted to maintain blood glucose at ~ 125 mg/dl based on samples collected every 10-60 minutes and measured on an automatic glucose analyzer. The infusion of ^{13}C -glucose will continue for ~ 82 hours. Cerebral ^{13}C -glycogen levels will be measured at $\sim 5, 12, 22, 34, 46, 58,$

70 and 82 hours after the end of the last hypoglycemic or euglycemic clamp. Blood samples will also be frozen for the later determination of plasma insulin concentrations by a chemiluminescent assay (Immulite, Diagnostic Products Corporation, Los Angeles, CA), and of the isotopic enrichment of the plasma glucose by gas-chromatography-mass spectroscopy (GC-MS) as described previously (40).

¹³C MRS methods:

¹³C-glycogen levels in the brain will be measured on a 4 T / 90 cm magnet (Oxford/Varian) using a quadrature 14 cm ¹H surface coil combined with a 9 cm diameter linear ¹³C coil (41). The [1-¹³C]glycogen NMR signal will be localized in a 7 × 5 × 6 cm³ voxel in the occipital lobe as described before (25). The amount of ¹³C label in the C1 position of glycogen will be quantified by the external reference method (23; 24). The [1-¹³C]glycogen concentrations will be divided by the plasma glucose isotopic enrichment (IE) to correct for differences in IEs between subjects and to determine the newly synthesized glycogen concentrations. ¹³C-glycogen levels will be corrected for the cerebrospinal fluid (CSF) content of the voxel (34).

Sample size justification and data analysis plan:

¹³C-glycogen levels will be compared following euglycemic preconditioning to following hypoglycemic conditioning with a repeated measures model with effects for precondition, acquisition time (5, 12, etc. hours), and their interaction; we will also test for an effect of the order of preconditioning. Correlation structures appropriate for doubly-repeated measures (across acquisition times within preconditioning, for two preconditioning sessions) will be used. Previous work (18) shows standard deviations of the group difference ranging from 0.2 to 0.4 μmol/g across the acquisition times, indicating that with 5 participants we will have 85% power to detect paired-group differences between 0.36 and 0.73 μmol/g with type I error of 5%. Per-acquisition-time group comparisons will be adjusted for multiple comparisons using Sidak's method. We have budgeted for 6 participants to allow for one failed study without sacrificing power. Since we have detected highly significant differences during and following single hypoglycemia vs. euglycemia in our prior studies with 5 subjects per group (18), we expect to be able to also detect a difference with 5 subjects who will serve as their own controls, if recurrent hypoglycemia does affect glycogen content/metabolism.

Potential pitfalls and solutions:

We have had success in recruiting subjects to participate in similar protocols in the past (18; 26) and all of the methods are well established in our laboratory. Thus, we do not anticipate any problems with the completion of the work. As in our previous work (18; 24; 26) glycogen content and turnover will be studied in the occipital lobe because of the low cerebral glycogen concentrations, the large size of the molecule that broadens its MR signal and the resulting small ¹³C MRS signal. It would be ideal to study hypothalamic glycogen levels and turnover; however this is not possible with the currently available technology and no other methods exist to monitor glycogen in the intact human brain.

As for aim 1a, we may find that the protocol we use to induce HAAF will not be effective for all subjects enrolled in the study. To ensure that HAAF is present at the time we examine glycogen metabolism, we will measure counterregulatory hormones in blood collected from subjects during the hypoglycemic clamps. If the epinephrine response (the hormone most blunted during most protocols in which HAAF is induced in humans (30; 31)) during the third hypoglycemic clamp is $\geq 70\%$ of the response measured during the first hypoglycemic clamp, we will conclude that HAAF was not induced and the data will not be used for analysis. If HAAF fails to be induced in 1/3, 2/5, 3/7, 4/9,... of the studies (we will monitor in an ongoing way), we will change the protocol to induce HAAF to include more episodes of hypoglycemia before the glycogen experiment.

Aim 2: To measure euglycemic and hypoglycemic GABA levels in the hypothalamus of subjects with type 1 diabetes and HAAF and in healthy volunteers preconditioned with euglycemia vs. recurrent hypoglycemia to induce HAAF.

In these experiments, subjects with type 1 diabetes and HAAF (as confirmed by counterregulatory hormone measurements during a hypoglycemic clamp), as well as normal controls with and without HAAF, will have hypothalamic GABA levels measured at a blood glucose of 95 mg/dl and again at a glucose level of 50 mg/dl by ¹H MRS at 7 tesla over a ~one hour period.

Study rationale:

Recent studies in animals suggest that hypothalamic GABA may be important in regulating the counterregulatory response to hypoglycemia and that elevated GABA levels may contribute to the development of HAAF (17). Recurrent hypoglycemia leads to increased basal GABA inhibitory tone in the ventromedial hypothalamus (VMH) and suppresses the counterregulatory response to subsequent episodes of hypoglycemia (16). The role of GABA in regulating the counterregulatory response and in the development of

HAAF in humans is unknown. Therefore, we will use our newly developed ^1H MRS methods to measure hypothalamic GABA in subjects with type 1 diabetes and HAAF and in healthy controls preconditioned with euglycemia vs. recurrent hypoglycemia to induce HAAF. We predict that hypothalamic GABA will be lower during hypoglycemia than euglycemia in controls and subjects with type 1 diabetes, that induction of HAAF will lead to an increase in hypothalamic GABA under both euglycemic and hypoglycemic conditions, and that subjects with type 1 diabetes and HAAF will have higher levels of hypothalamic GABA under both euglycemic and hypoglycemic conditions than euglycemia preconditioned controls (Fig. 7). The MRS acquisition protocol will also provide concentrations of the precursor of GABA, glutamate (Fig. 1), which will potentially provide supporting information about GABA metabolism, however our hypotheses are based on GABA levels, which have been reported to change in prior animal work.

[figure not shown]

Figure 7. Predicted changes in eu- and hypoglycemic GABA levels in hypothalamus (as in Fig. 4) in the healthy brain and in HAAF.

Research Subjects:

Recruitment strategies and inclusion and exclusion criteria will be identical to those in Aim 1a, except we will also exclude subjects who take drugs that can alter GABA metabolism (such as benzodiazepines).

Study Protocol:

Subjects will report to the Center for Magnetic Resonance Research in the morning in the fasting state. *Subjects with diabetes* will be instructed to manage their diabetes in such a way as to minimize the amount of subcutaneous insulin present at the time of study while maintaining adequate control. *Healthy subjects* will serve as their own controls and be studied following the Day 1 hypoglycemia and euglycemia preconditioning protocols described for Aim 1 (Fig. 8). At least six weeks will separate the two studies, which will be done in random order. Female controls will have their two studies two months apart in order to control for phase of menstrual cycle.

On the day of the MRS experiment, an intravenous catheter will be placed antegrade in a forearm for subsequent infusions and a catheter will be placed retrograde in the lower leg for blood sampling. Patients with diabetes will be started on a variable rate infusion of intravenous insulin designed to bring their blood glucose to 95 mg/dl. To adjust the rate, blood will be collected every 5 minutes and tested on a nearby Analox machine. The experiment will begin, for both patients and controls, when the subject is at euglycemia. At time 0, insulin will be started at a rate of 2.0 mU/kg/min, potassium phosphate will be started at a rate of 4 mEq/hr, and glucose (20% dextrose) will be administered at a variable rate to maintain the blood glucose at 95 mg/dl. Subjects will then be placed into the 7 tesla magnet and hypothalamic GABA will be measured. At +60, blood glucose will be reduced to 50 mg/dl. The time course for hypothalamic GABA will be measured as shown in Fig. 4. Samples for the measurement of glucagon, epinephrine, norepinephrine, cortisol, and growth hormone will be collected at minutes 0, 60, 90, and 120. At the completion of the measurement, subjects will be taken out of the magnet, blood glucose will be restored, and subjects will be fed.

^1H MRS methods:

Spectra will be acquired and quantified using identical methods to those described in Aim 1a. We chose to utilize STEAM spectroscopy to quantify GABA levels, as opposed to edited spectroscopy, since the GABA quantification using STEAM was validated against edited spectroscopy (42) and STEAM provides better signal-to-noise and additional metabolite concentrations such as glutamate (the precursor of GABA) and glucose (see Potential pitfalls for Aim 1a).

Sample size justification and data analysis plan:

[figure not shown]

Figure 8. Study protocol for healthy controls in Aim 2.

Euglycemia vs. hypoglycemia states: After preconditioning with euglycemia among the controls, GABA levels will be compared during euglycemia to during hypoglycemia with a repeated measures model with effects for glycemic state, acquisition time (5, 15, etc. minutes, Fig. 4), and their interaction. Correlation structures appropriate for doubly-repeated measures (across acquisition times within glycemic states, for two glycemic states) will be used. These comparisons will be repeated among the controls after preconditioning with hypoglycemia, and among the patients. Pilot work (Fig. 4) shows a standard deviation of the control group difference between euglycemic states and hypoglycemic states of 0.52 $\mu\text{mol/g}$, indicating that with 10 participants we have 85% power to detect paired-group differences of 0.53 $\mu\text{mol/g}$ with type I error of 5%. In the case that standard deviations are twice those observed in Figure 4, we have 85% power to detect differences of 1.10 $\mu\text{mol/g}$. Per-acquisition-time glycemic state comparisons will be adjusted for multiple comparisons using Sidak's method. We have budgeted for 12 participants to allow for two failed scans without sacrificing power. *Patients vs. controls:* Similar comparisons will be carried out between GABA levels in patient euglycemia states and in control euglycemia states after the controls are euglycemic preconditioned. This will be repeated for GABA in hypoglycemic states. Pilot work (Fig. 4) shows a standard deviation of the control group minus patient group difference during the hypoglycemic state of 0.25 $\mu\text{mol/g}$, indicating that with 10 participants we have 85% power to detect paired-group differences of 0.27 $\mu\text{mol/g}$ with type I error of 5%. In the case that standard deviations are twice those observed in Figure 4, we have 85% power to detect differences of 0.53 $\mu\text{mol/g}$. *Preconditioning:* Similar comparisons will be carried out between GABA levels during control euglycemia states for euglycemic preconditioning compared to hypoglycemic preconditioning. This will be repeated for GABA during hypoglycemic states.

Potential pitfalls and solutions:

Prior rodent studies that demonstrated a role for increased hypothalamic GABA tone in blunting the counterregulatory response to hypoglycemia studied the VMH, while our spectroscopic voxel contains a larger portion of the hypothalamus. Despite this pitfall, our preliminary data demonstrate our ability to measure the hypothalamic GABA response to hypoglycemia both in controls and patients with type 1 diabetes. Therefore, we expect to be able to address our hypotheses regarding hypothalamic GABA despite these partial volume effects.

As discussed above, one potential problem we may encounter is that the protocol we use to induce HAAF will not be effective for all subjects enrolled in the study. To ensure that HAAF is present at the time we examine GABA metabolism, we will measure counterregulatory hormones in blood collected from subjects during hypoglycemia. If the epinephrine response (the hormone most blunted during most protocols in which HAAF is induced in humans) during the study done after hypoglycemic preconditioning is $\geq 70\%$ of the response measured during the study after euglycemic preconditioning, we will conclude that HAAF was not induced and the data will not be used for analysis. If HAAF fails to be induced in 1/3, 2/5, 3/7, 4/9,... of the studies (we will monitor in an ongoing way), we will change the protocol to induce HAAF to include more episodes of hypoglycemia before the GABA experiment. In addition, in this aim the blunted counterregulation will also be confirmed in patients with type 1 diabetes by comparing their hormone measurements during the hypoglycemic clamp to those of the euglycemia-preconditioned controls.

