Study Title: Measurement of Glucose/Glycogen Metabolism in Humans Using
Magnetic Resonance at 4 or 7 Tesla

PI: [name]

NCT00786825

IRB 9412M09040

Revised: 9/30/2011

SPECIFIC AIMS

The fear of hypoglycemia and hypoglycemia unawareness limits the ability of patients with diabetes from achieving the level of glucose control known to reduce the risk of developing microvascular complications. The **long term goal** of this project is to define the pathogenesis of hypoglycemia-associated autonomic failure (HAAF) with the aim of helping patients better manage their diabetes. In HAAF, patients experience both *hypoglycemia unawareness* and *defective glucose counterregulation*. Increased glucose availability to the brain is a likely contributor to the development of *hypoglycemia unawareness* either by increased glucose transport, decreased glucose utilization or increased glycogen storage following repeated episodes of hypoglycemia. Work previously supported by this award provided evidence for elevated free glucose levels in cortical regions of patients with type 1 diabetes and hypoglycemia unawareness, but the impact of recurrent hypoglycemia on glucose levels and metabolism in the hypothalamus, the region in which both glucose sensing and coordination of the counterregulatory response are believed to occur, has not been evaluated. Growing evidence in animal models and humans also suggests that increased hypothalamic γ -aminobutyric acid (GABA) tone following recurrent hypoglycemia plays a central role in *defective glucose counterregulation*, but hypothalamic levels of GABA have not yet been measured in humans with and without HAAF. We recently developed in vivo proton magnetic resonance spectroscopy (^1H MRS) methodology to monitor glucose and GABA levels in the human hypothalamus at the ultra-high magnetic field of 7 tesla and to simultaneously measure all 4 kinetic parameters for cerebral glucose transport and utilization (K_M transport, V_{\max} transport, K_M utilization, V_{\max} utilization). These methods will now be employed in humans together with the ^{13}C -MRS protocol we have previously used to study brain glycogen to examine if changes in glucose availability (in the form of free glucose or glycogen) and GABA levels contribute to the development of *hypoglycemia unawareness* and *defective glucose counterregulation* in HAAF.

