The **working hypotheses** for this project are: **1)** recurrent hypoglycemia, like that seen in subjects with type 1 diabetes and iatrogenic hypoglycemia, will lead to an upregulation of glucose availability for the brain (by increased transport, and/or increased glycogen storage), thereby facilitating maintenance of cerebral metabolism during subsequent episodes of hypoglycemia, and **2)** recurrent hypoglycemia will lead to an increased GABA tone in hypothalamus, thereby suppressing glucose counterregulation during subsequent episodes of hypoglycemia. To address these hypotheses we will examine cerebral metabolism in subjects with type 1 diabetes and hypoglycemia unawareness, as well as in healthy volunteers preconditioned with euglycemia vs. recurrent hypoglycemia to induce HAAF, thereby permitting us to understand the clinical syndrome as well as isolate the effects of recurrent hypoglycemia from those induced by diabetes.

Aim 1: To determine the contribution of increased glucose availability in the brain to HAAF

Specific Aim 1a: To measure kinetic parameters for glucose transport and metabolism in the hypothalamus of subjects with type 1 diabetes and hypoglycemia unawareness and in healthy volunteers preconditioned with euglycemia vs. recurrent hypoglycemia to induce HAAF.

Hypothesis 1a.1: Subjects with type 1 diabetes and hypoglycemia unawareness will have a higher V_{\max} transport than will healthy volunteers preconditioned with euglycemia.

Hypothesis 1a.2: Healthy volunteers will have a higher V_{\max} transport following preconditioning with recurrent hypoglycemia than with euglycemia.

Specific Aim 1b: To measure brain glycogen turnover and content by ^{13}C MRS in healthy volunteers preconditioned with euglycemia vs. recurrent hypoglycemia to induce HAAF.

Hypothesis 1b: Subjects will have higher glycogen content following preconditioning with recurrent hypoglycemia than with euglycemia.

Aim 2: To determine the contribution of increased GABA tone in the hypothalamus to HAAF

Specific Aim 2: To measure euglycemic and hypoglycemic GABA levels in the hypothalamus of subjects with type 1 diabetes and HAAF and in healthy volunteers preconditioned with euglycemia vs. recurrent hypoglycemia to induce HAAF.

Hypothesis 2a: Hypothalamic GABA levels will be lower during hypoglycemia than during euglycemia in both normal controls and patients with type 1 diabetes.

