These data demonstrate our ability to reliably measure GABA and glucose concentrations for the proposed studies in Aims 1a and 2 and support our hypothesis regarding an attenuated hypothalamic GABA response to hypoglycemia in type 1 diabetes and hypoglycemia unawareness.

[figure not shown]

Figure 4. Plasma glucose and hypothalamic GABA concentrations in a healthy volunteer (A) and a patient with type 1 diabetes (B) during a hypoglycemic clamp study. Subjects received IV infusions of glucose and insulin. The glucose infusion was stopped at time 0 and restarted later at a lower rate to clamp subjects at 50mg/dl plasma glucose. The healthy volunteer was also studied in a separate session during euglycemia without IV infusions (green circles, A).

C.2. RESEARCH DESIGN

Aim 1a: To measure kinetic parameters for glucose transport and metabolism (K_M transport, V_{max} transport, K_M utilization, V_{max} utilization) in the hypothalamus of subjects with type 1 diabetes with hypoglycemia unawareness and in healthy volunteers preconditioned with euglycemia vs. recurrent hypoglycemia to induce HAAF.

In these experiments, subjects with type 1 diabetes with hypoglycemia unawareness as well as normal controls, preconditioned on separate occasions with euglycemia and with recurrent hypoglycemia, will have hypothalamic glucose concentrations measured continuously using ^1H MRS at 7 tesla over a ~1.5 hour period during which blood glucose concentrations will be experimentally increased from 95 mg/dl to one of 3 target hyperglycemic levels (200 mg/dl (11 mM), 300 mg/dl (16.5 mM), 400 mg/dl (22 mM)).

Study rationale:

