V_{max}^t will be compared between patients and euglycemia conditioned controls with a paired t-test; if data are highly skewed, non-parametric alternatives will be considered. Similar comparisons will be carried out, within the controls, between the results following euglycemic preconditioning and following hypoglycemic conditioning. Pilot data standard deviation in V_{max}^t (section C1.2) indicate that with 12 participants per group we have 85% power to detect paired-group differences of 14% in V_{max}^t with type I error of 5%. We have budgeted for 15 per group to allow for some failed scans without sacrificing power. Our previous data in the occipital cortex demonstrated ~17% higher glucose concentrations in subjects with type 1 diabetes and hypoglycemia unawareness vs. controls. Therefore, we expect to be able to detect a similar effect size in the hypothalamus in the proposed studies with 12 subjects in each group. While our power calculations are based on SD in V_{max}^t because we hypothesize that unidirectional glucose transport is upregulated in HAAF, our studies will also be able to reveal a change in V_{max}^{util} , if HAAF involves a change in glucose metabolism, thanks to the simultaneous measurement of these parameters with the new modeling approach.

Potential pitfalls and solutions:

Data will be collected as blood glucose is experimentally increased from 95 to 200, 300, or 400 mg/dl and we assume that the same kinetic constants will apply under hypoglycemia conditions. Under Aim 2, we will also obtain hypothalamic glucose data under hypoglycemia because we will be using the same MRS methods to obtain neurochemical profiles in these two aims. Since these data will also be available, we will assess the reliability of hypothalamic glucose measurements at hypoglycemia at a lower time resolution than that shown in Fig. 2B, e.g. in spectra acquired every 10-20 minutes instead of every 2.5 min. Because we save our MRS data in single shots, we can process these data to add over different time windows. Indeed, such lower time-

resolution data may also provide hypoglycemic glucose concentrations in hypothalamus. However, we chose to design the primary experiments under Aim 1a with hyperglycemic targets which we know will provide us with the kinetic parameters with certainty.

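### The Aim 1a sample size is supported by a 17% glucose difference although the test is on V_max transport, where the same effect is probably below the detectable 14%; hypothalamic glucose itself is never compared

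*Combined protocol and SAP*

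**What the plan says.** The heading of the first aim reads "Aim 1: To determine the contribution of increased glucose availability in the brain to HAAF". The opening Specific Aims paragraph describes the target as "changes in glucose availability (in the form of free glucose or glycogen", closing the bracket there. Working hypothesis 1 is more mechanistic: recurrent hypoglycemia "will lead to an upregulation of glucose availability for the brain (by increased transport, and/or increased glycogen storage", again closing the bracket. Hypotheses 1a.1 and 1a.2 are worded only in terms of V_max transport.

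Under C.2, Aim 1a, subjects "will have hypothalamic glucose concentrations measured continuously" while plasma glucose is raised to 200, 300 or 400 mg/dl. Research Subjects gives the matched control the patient's target. Study Protocol expects brain glucose to hold at steady state for at least 20 minutes.

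In the Aim 1a sample size section, V_max transport "will be compared between patients and euglycemia conditioned controls with a paired t-test", and the two control sessions are compared in a similar way. The plan states that "with 12 participants per group we have 85% power to detect paired-group differences of 14" percent, "with type I error of 5" percent. It continues: "Our previous data in the occipital cortex demonstrated ~17% higher glucose concentrations in subjects with type 1 diabetes and hypoglycemia unawareness vs. controls". From this it expects to detect an effect of similar size in the hypothalamus with 12 per group. V_max utilization is mentioned as something the study could reveal, without a test or power.

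**The concern.** There are two gaps.

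First, the sample size argument changes variable. The 17% is a difference in glucose concentration, while the 14% is a difference in V_max transport. A percentage change in one is not the same percentage change in the other. If the 17% is read as a V_max effect, it lies comfortably above 14%. If it is read as a glucose effect, the plan has no glucose test to which the power applies. Either way, the reassurance does not follow.

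Second, for the free-glucose half of availability, Aim 1a tests one determinant of brain glucose and not brain glucose itself. Aim 1b covers glycogen. A rise in V_max transport matched by a rise in utilization would confirm the hypotheses as worded, but would not show more glucose in the hypothalamus. The data that would settle this are collected and used only as input to the kinetic fit.

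**Working it through.** **Inputs from the documents.** Pilot V_max transport 0.94 ± 0.21 and V_max utilization 0.48 ± 0.12 µmol/g/min (C.1.2: occipital cortex, 4 tesla, 5 volunteers). Plasma targets 11, 16.5 and 22 mM (C.2, Aim 1a). The kinetic equation (Modeling methods). n = 12, 85% power, 14%, type I error 5%.

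**Assumed, because not given.** K_M transport 0.5-3 mM; two-sided testing; cortical pilot values carried over to the hypothalamus.

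**1. The plan's 14%.** For a two-sided paired t-test with 12 pairs and 85% power, the noncentral t distribution gives a detectable difference of 0.951 SD of the paired difference. The same formula with 5 pairs gives 1.807 SD, or 0.36 and 0.72 µmol/g for SDs of 0.2 and 0.4, against 0.36 and 0.73 stated in Aim 1b, so the method fits the plan.
- SD needed for 14%: 14 / 0.951 = 14.7%.
- Pilot CV: 0.21 / 0.94 = 22.3%. Used as the SD of the difference, it gives 0.951 × 22.3 = 21.2%, not 14%.
- With SD of difference = CV × √(2(1 − ρ)), 14.7% needs a within-pair correlation ρ of about 0.78, which the plan does not state.

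Both SDs are carried forward.

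**2. Converting 17% glucose to V_max transport.** At steady state, transport equals consumption C. Let g be brain glucose divided by V_d, P plasma glucose, K the K_M for transport and V the V_max for transport:

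V(P − g)/(K + P + g) = C, so with r = C/V, g = [P(1 − r) − rK]/(1 + r).

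V_d cancels from percentage changes. For a new level g′ = 1.17g, r′ = (P − g′)/(P + g′ + K) and V′ = C/r′.

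Example at P = 11, K = 3, C = 0.48: r = 0.48/0.94 = 0.511, g = 2.549, g′ = 2.983, r′ = 8.017/16.983 = 0.472, V′ = 1.017. The rise is 1.017/0.94 − 1 = 8.2%.

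Rise in V_max transport that gives 17% more glucose:

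| C (µmol/g/min) | K_M transport (mM) | 11 mM | 16.5 mM | 22 mM |
|---|---|---|---|---|
| 0.48 | 0.5 | 12.4% | 12.7% | 12.9% |
| 0.48 | 1.5 | 10.6% | 11.5% | 11.9% |
| 0.48 | 3 | 8.2% | 9.7% | 10.6% |
| 0.40 | 0.5 | 17.3% | 17.7% | 17.9% |
| 0.40 | 3 | 12.5% | 14.3% | 15.2% |

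At consumption 0.48 the range is about 8-13%, all below 14%. At 0.40 it is about 12-18%, on both sides of 14%.

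**3. Power with 12 pairs (noncentral t, two-sided 5%).**

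| True rise in V_max transport | SD 14.7% | SD 22.3% |
|---|---|---|
| 8.2% | 42% | 21% |
| 10% | 57% | 29% |
| 12.9% | 79% | 45% |
| 17% (if glucose and V_max were interchangeable) | 95% | 67% |

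**4. V_max transport and brain glucose.** Multiply both V_max values by the same factor k. The right side of the model equation becomes k times its former value, so it is zero at the same brain glucose. The plateau is unchanged whatever the two K_M values. With the other parameters fixed, V_max transport does drive glucose: under the assumptions of step 2 with C = 0.48, a 14% rise gives about 18-28% more.

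**5. What a glucose comparison could detect.** The documents give no SD of paired hypothalamic glucose differences. With 12 pairs, power for a 17% difference is about 95% at an SD of 15%, 76% at 20% and 43% at 30%. The only hypothalamic test-retest figure is a glucose CV of 20%, from one volunteer at euglycemia (C.1.4). If it carried over, the paired SD would be 20% × √2 = 28% and power about 48%.

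**The case against.** The strongest reply is that test and hypothesis agree. Hypotheses 1a.1 and 1a.2 concern V_max transport, and the analysis tests exactly that. The choice is argued: Study rationale says that higher steady-state glucose has already been shown in cortex, and moves to dynamic data to look at transport and metabolism directly. Working hypothesis 1 ties availability to transport. The kinetic constants are also assumed to hold under hypoglycemia, which a plateau at 200-400 mg/dl does not measure. All of this stands, and V_max transport should stay primary.

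A reader might infer that V_max transport is the wrong endpoint, or that plateau glucose is much more precise and should come first or act as gatekeeper. The documents do not support that. Averaging spectra over 20 minutes reduces measurement noise, but the per-spectrum noise at hyperglycemia is not given. Biological variation can also reverse the ranking. With an assumed independent 10% biological CV in each V_max, consumption equal to V_max utilization and K_M transport 0.5-3 mM, plateau glucose has a CV of about 20-31%. The 18-28% glucose response to a 14% V_max rise is then about 0.9 SD, against 14/10 = 1.4 SD for V_max transport.

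A rise in both V_max values would not be a false confirmation of 1a.1 or 1a.2 either, since transport would really have risen. The care is needed in the step from that result to availability.

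Finally, the conversion depends on consumption. If utilization is well short of saturation, so that consumption falls below 0.48, the required rise can pass 14%.

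**Conclusion.** The point holds in two limited parts.

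First, the 17% glucose figure does not support the stated power for V_max transport. At consumption 0.48 and K_M transport 0.5-3 mM it corresponds to about 8-13%, below the stated detectable 14%. Power is about 42-79% at the plan's implied SD and 21-45% at the pilot CV, whereas reading the 17% directly on the V_max scale would suggest 95% and 67%. At consumption 0.40 the corresponding rise is about 12-18%, so the shortfall is likely but not certain. The figures rest on the plan's model, cortical pilot values from five people, an assumed K_M range and two-sided testing.

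Second, Aim 1a plans no comparison of the hypothalamic glucose it measures. A V_max transport result alone therefore cannot show that free glucose is more available. This is a gap between Hypotheses 1a.1 and 1a.2 and the Aim 1 question, not an error in the test of those hypotheses. It does not establish that glucose would be the more powerful endpoint.

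**What to change.** 1. In the Aim 1a sample size section, delete the inference from 17% higher glucose. Otherwise restate it on the V_max transport scale, with the K_M and consumption ranges assumed and the resulting power.
2. Keep V_max transport as the primary test of Hypotheses 1a.1 and 1a.2. Add a prespecified secondary paired comparison of mean hypothalamic glucose over the last 20 minutes at target: patients against euglycemia-preconditioned controls, and hypoglycemia against euglycemia preconditioning within controls. Analyse within-pair log ratios, allowing for target and for the within-pair difference in plasma glucose over the same window. Pool across targets, since 12 to 15 pairs over three targets leave only about 4 to 5 at each.
3. State that a rise in V_max transport will be read as increased free-glucose availability only together with this comparison and the V_max utilization result.

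The cost is protocol wording and one further analysis of data already collected, with no extra scan, visit or participant. The sponsor would also have to state a less favourable expectation for V_max transport, and should say that power for the glucose comparison is unknown until a paired SD is available.
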